3.3 Index and reference tests

3.3.1 Index test

The international electronic-Delphi exercise involving expert health professionals and patients (see section 1.3 for further detail) has identified a list of 17 diagnostic features which were agreed to be 'critical', or 'important but not critical' in the diagnosis of LS. The SHELLS diagnostic test accuracy study is using this list of 17 diagnostic features as the index test.

A diagnostic criteria assessment looking for the presence or absence of these 17 diagnostic features, using experience and clinical judgement, will be performed by an assessor blinded to the reference standard (specialist's diagnosis – see section 3.3.2).

List of diagnostic features to be assessed as part of the index test:

Critical:

- Changes in the anatomy of the genital area
- Response to topical corticosteroids
- Whiteness
- Itch
- Burying of the clitoral area

Important but not critical:

- Absence of vaginal involvement
- Fissuring
- Crinkly skin
- Bruising/bleeding under the skin
- Fissuring at the back entrance to the vagina
- Pain/soreness unrelated to sexual activity
- Pain/soreness related to sexual activity
- Skin thickening
- Loss of skin stretchiness

- Erosions
- Irritation
- Perianal fissure

3.3.2 Reference standard

Specialist's diagnosis as recorded in the participant's medical record. The diagnosis is a clinical diagnosis and may include, but does not require, a skin biopsy. This diagnosis is undertaken as part of the patient's usual care.

3.4 Study flow

This is a cohort cross-sectional study, including consecutive new patients presenting with a vulval skin complaint to a specialist outpatient clinic (see under 'Setting' – section 3.2 for types of clinic). The patient flow through the study is depicted in Figure 1.

4 STUDY MANAGEMENT

The Chief Investigator has overall responsibility for the study and shall oversee all study management.

The data custodian will be the Chief Investigator.

This study will be managed from the Centre of Evidence Based Dermatology at the University of Nottingham by [name], Associate Professor and Consultant Dermatologist as part of her NIHR Advanced Fellowship. [name] will be supported by [name] (Co-Director of the Centre of Evidence Based Dermatology), [name] (Professor of Clinical Trials) and [name] (study statistician). A Research Assistant will be supporting [name] with the running and coordination of the study. There will be regular meetings to ensure adequate progress and address any rising issues. These are likely to be monthly to begin with but may decrease in frequency once the study is smoothly up and running.

Research data management & collection will be supported through the University of Nottingham's Clinical Database Support Service and their locally hosted/managed REDCap platform.

A Research Assistant will support the co-ordination of the multicentre study in terms of obtaining relevant approvals, site initiation, data management and overall administration. In addition, Nottingham Clinical Trials Unit (NCTU) will supervise the Research Assistant with regards to these aspects.

A study management group including patients, clinical experts, methodologists and an independent advisor will oversee the research. This group will meet at least quarterly.

4.1 Duration of the study and participant involvement

Study Duration: The study will last for approximately 24 months overall, with the possibility for extension if participant recruitment is slow. Participant enrolment will begin once HRA and REC approvals have been obtained and all site approvals are in place.

Participant Duration: Participants will be involved at the point of consent to the study until the diagnostic criteria assessments have been completed. Participants will have one study visit that will last approximately 30 minutes. There will be no follow up appointments related to the study.

4.2 End of the Study

The end of the study will be the last study visit of the last participant.

5 SELECTION AND WITHDRAWAL OF PARTICIPANTS

5.1 Recruitment

- Potential participants will be consecutive new patients referred with a vulval skin complaint to a specialist outpatient clinic (types of clinic are detailed in section 3.2).
- They will be identified from clinic lists by the usual care team.
- The study participant information sheet (PIS) will be sent in advance of their outpatient appointment via letter of invitation, or text message with a link to the PIS (depending upon site specific processes for contacting patients).
- Interested patients will complete an online expression of interest form following which the local site research team will contact the patient to answer any questions and discuss potential participation. They can also contact the local site research team via telephone if preferable to the patient (i.e patient doesn't want to click on the link or QR code in the PIS).
- Following discussion with the local site research team, if willing to participate, the patient can complete consent online in advance of their appointment. If not completed in advance, they can complete consent at the time of their face-to-face scheduled clinic appointment.
- On attendance at the face-to-face outpatient appointment:
 - Those **who have already consented** to participate in the study will have consent confirmed by a member of the research team. They will undergo their usual consultation (history and examination) plus a second examination by a blinded trained assessor. Participants who are from the Nottingham centre may also receive a third examination. This is to assess whether two different professionals using the diagnostic criteria agree on the same diagnosis. A member of the research team will collect additional information and enter this onto the CRFs.
 - Those **who have not yet consented** will be given the opportunity to discuss their participation further with a member of the research team. If willing, they will complete online/paper consent and they will go on to have their usual consultation plus a second examination by a blinded trained assessor. Participants who are from the Nottingham centre may also receive a third examination. This is to assess whether two different professionals using the diagnostic criteria agree on the same diagnosis. A member of the research team will collect additional information and enter this onto the CRFs.
 - Examinations by both the managing clinician **and** the blinded assessor must be completed for inclusion in the study.
 - If needed, hospital interpreter and translator services will be available to assist with the discussion of the study, the participant information sheets and consent forms. The consent forms and information sheets however will not be available in other languages.
 - Those who do not consent will have their usual clinical consultation. They will be made aware that their care will not be affected by their decision to decline participation in the study.

- Those who are unsure and request more time to consider the study will have their usual clinical consultation. If at a later stage they decide to participate, they will provide consent online and the research team will invite them to attend a research visit where information to complete CRFs will be collected in addition to an examination by a blinded assessor. In this situation, participation will only be possible if patients can return for a research appointment **within two weeks of the initial consultation at the specialist clinic.**

Those who do not receive information prior to their scheduled outpatient consultation will be approached on the day by their usual care team to provide information and invite for discussion with the research team regarding the study.

Posters and flyers will also be visible in outpatient clinics for patients to view which detail links and a QR code for further study information.

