5.2.2 Exclusion criteria

- Inability to provide informed consent
- Patients with surgical alteration of vulval skin as part of gender reaffirming surgery, or patients not born with a vulva
- More than 2 weeks since initial consultation from managing clinician

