5.5 Informed consent

Informed consent will be obtained in accordance with the Research Ethics Committee guidance and Good Clinical Practice. Participant information will be developed involving patient representatives to ensure it is clear and easily understood. Potential participants will be allowed sufficient time to consider their participation. Same day research appointments will be available, but if patients request additional time to consider their involvement this will also be possible. The PIS will also cover what happens if a patient wishes to withdraw from the study.

All participants will provide written or digital informed consent. The Informed Consent Form will be signed and dated by the participant before entering the study. The Investigator or their nominee will explain the details of the trial and provide a PIS (either in advance of, or at the time of the outpatient clinic visit), ensuring that the participant has sufficient time to consider participating. The Investigator or their nominee will answer any questions that the participant has concerning study participation. As the study is low risk due to being non-interventional, we believe there will be sufficient time to consider participation for those who receive the PIS on the same day as their outpatient visit. This has the added benefit of being more convenient than coming back for another visit. However, potential participants will be given the opportunity to return on another occasion, within the next two weeks, if they wish (Figure 1).

If needed, hospital interpreter and translator services will be available to assist with the discussion of the study, the participant information sheets, and consent forms, but the consent forms and information sheets will not be available in other languages.

Clinical photographs will be taken as part of normal medical care. Participants will be asked specifically for consent to use the photographs for research purposes for development of a training manual which will be used at a later stage alongside the diagnostic tool to support its use.

Informed consent will be obtained from each participant before they undergo physical examination and have information collected for the study. Consent will primarily be completed online, but where a paper version is completed, this will be scanned and uploaded to REDCap. The participant will be provided a copy of this and it will be recorded in the medical record that consent for the study has been obtained.

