6. REGIMEN

6.1 Patient pathway – Assessments

- Participants will receive a clinical assessment from their usual managing clinician as part of their usual outpatient appointment. This will involve a physical examination and routine clinical questions.
- A blinded assessor (for example, Trainee, Clinical Fellow, Specialist Nurse) will then examine the patient and record clinical diagnostic features on the CRF. A third assessor who is also blinded may also examine the patient at the Nottingham site. Participants can opt out of examination by two different professionals if they wish, but to participate in SHELLS they must agree to at least one additional examination.
- The blinded assessor will be asked to examine the patient without speaking to the managing clinician. The managing clinician will ensure that the clinical notes are closed

and unable to be viewed by the blinded assessor as they come in the room, and REDCap (Research Electronic Data Capture) will disable access to the clinician diagnosis by the blinded assessor. The patient will be advised not to give any information to the blinded assessor/s other than specific questions that are asked in relation to the research.

- The blinded assessment will ideally take place immediately after the managing clinician has examined the patient. This will prevent disruption of flow to patients coming through the clinic and it will prevent patients from having to get undressed twice.
 - However, we acknowledge that flexibility is required and each site may need to adapt their own flow for how the clinical assessments are performed, ensuring blinding of the additional assessor/s.
- Information collected by the research team (not the blinded assessor) for each participant will include:
 - Age
 - Ethnicity
 - Post code (for socioeconomic status)
 - Participant rating of the condition on the day of assessment
 - Physician global assessment of disease severity (assessed and recorded by managing clinician)
 - Symptom duration
 - Diagnosis of LS prior to clinic appointment
 - Previous diagnosis of a vulval condition (Y/N and what diagnosis)
 - Treatments received (Y/N and what treatment)
 - Treatment duration
 - Whether on active treatment at time of recruitment (Y/N)
 - Whether the patient has 'early or late' stage LS (assessed and recorded by managing clinician)
 - Presence or absence of each of the individual diagnostic features (Index test, see section 3.3.1)

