8 ADVERSE EVENTS

The occurrence of an adverse event as a result of participation within this study is not expected and no adverse event data will be collected. Patients will have their vulval condition diagnosed in line with usual clinical practice. They will be treated by their managing clinician based on the clinician diagnosis (reference standard), not based upon the Delphi-agreed diagnostic criteria (index test). If the clinician diagnosis is amended at a later stage, this will be recorded in the SHELLS database and their management will be amended according to usual practice.

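### For late deciders the index features may be recorded up to two weeks after the reference diagnosis, with treatment in between, so some features, above all steroid response, can be altered by that diagnosis

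*Protocol*

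**What the plan says.** The reference standard is the specialist's diagnosis made in usual care (Protocol 3.3.2). The index test is a blinded assessor's record of 17 features (3.3.1).

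- **Order and gap.** Protocol 5.1: "Those who are unsure and request more time to consider the study will have their usual clinical consultation". If they later agree, they attend a research visit where "information to complete CRFs will be collected in addition to an examination by a blinded assessor", provided this is "within two weeks of the initial consultation at the specialist clinic". Section 5.5 repeats the option: "potential participants will be given the opportunity to return on another occasion, within the next two weeks, if they wish". Section 5.2.2 excludes only beyond that point: "More than 2 weeks since initial consultation from managing clinician".
- **Preferred timing.** Sections 6.1 and 6.2 aim for the blinded examination straight after the clinician's, or as soon as can be managed, but do not require the same day.
- **Treatment.** Section 8 (Adverse Events): "They will be treated by their managing clinician based on the clinician diagnosis (reference standard". It adds that the index criteria do not guide treatment.
- **Index features.** Section 3.3.1 lists "Response to topical corticosteroids" among the five critical features and gives no period to which the response refers. Itch, irritation, fissuring and erosions are also listed.
- **Data collected.** Section 6.1 lists treatments received, treatment duration and "Whether on active treatment at time of recruitment (Y/N". It lists no item for treatment started between the two examinations.
- **Analysis.** Section 7.1 enters all criteria into one backward logistic regression and uses all development data. It draws no distinction by interval or by treatment in the interval.

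**The concern.** An accuracy study needs the two tests to describe the same patient in the same state, and needs the reference result to have no path into the index result. For late deciders such a path exists: the reference diagnosis leads to treatment, and treatment can change the recorded features.

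The two effects run in opposite directions. A reversible feature that eases in treated LS patients loses apparent sensitivity and may be dropped or under-weighted by the backward selection. Steroid response can gain association with LS that it would not have for the intended users, who would apply the tool before any specialist has diagnosed or prescribed. Because treatment depends on the diagnosis, neither error need be equal in the LS and non-LS groups.

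The blinding in 6.1 hides the diagnosis from the assessor. It does not stop treatment from changing what the assessor sees or is told.

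**Working it through.** The protocol states no figure on this point, so there is none to reproduce. The arithmetic below shows scale only.

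**Inputs from the protocol**
- Gap of up to 14 days (5.1, 5.2.2, 5.5).
- Remission in 70% over three months on first-line treatment (1.2), taken as 91 days.
- 185 LS and 185 non-LS patients (7.2).

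**Assumed inputs**
- Delayed share d: 10% and 30%.
- True sensitivity of a reversible feature: s = 0.80.
- Same-day steroid response recorded as yes in 30% of both groups, so the true odds ratio is 1.
- Share w of delayed LS patients otherwise recorded as no who become yes: 20% to 80%.
- All delayed LS patients treated for the full interval; non-LS patients unchanged.

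**Two-week clearance r, treating remission as a proxy for a feature clearing**
- Linear: 0.70 × 14/91 = 0.108.
- Constant rate: 1 − 0.30^(14/91) = 0.169.

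**Reversible feature:** apparent sensitivity = s(1 − d·r); LS patients changing from present to absent = 185·d·s·r.

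| d | r | Apparent sensitivity | Patients changed |
|---|---|---|---|
| 10% | 0.108 | 0.791 | 1.6 |
| 10% | 0.169 | 0.786 | 2.5 |
| 30% | 0.108 | 0.774 | 4.8 |
| 30% | 0.169 | 0.759 | 7.5 |

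**Steroid response:** P(yes | LS) = 0.30 + 0.70·d·w, against 0.30 in non-LS, whose odds are 0.30/0.70 = 0.429.

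| d | w | P(yes given LS) | Spurious odds ratio |
|---|---|---|---|
| 10% | 20% | 0.314 | 1.07 |
| 10% | 80% | 0.356 | 1.29 |
| 30% | 20% | 0.342 | 1.21 |
| 30% | 80% | 0.468 | 2.05 |

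For example, at d = 30% and w = 80%: (0.468/0.532)/0.429 = 2.05.

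**The case against.** The strongest reply is that this is an exception with a cap. Information goes out before the appointment, consent is taken before or at it, and only patients who ask for more time use the return visit. The option protects consent, and the two-week limit itself restrains change. No delayed share is given, so neither 10% nor 30% has support in the protocol. That stands, and it limits the size of the point.

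Other parts also stand:
- The loss for reversible features is small against sampling error. With 185 LS patients, the standard error of a sensitivity of 0.80 is √(0.80 × 0.20/185) = 0.029; the shifts above run from 0.009 to 0.041.
- Section 1.1 calls scarring irreversible. Anatomical change and burying of the clitoral area, two of the five critical features, are not exposed.
- Treated non-LS patients may change too, which could partly offset both effects.
- For late deciders, treatment duration is collected at the return visit, so a duration shorter than the gap might reveal newly started treatment.
- Sensitivity analyses may be in a SAP, which was not available.

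These do not remove the point. Treatment duration does not say which treatment a recorded response refers to. The two-week window and the undefined steroid-response feature are set in the protocol itself.

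A reader might infer that many signs disappear within the fortnight, for example in half of delayed LS patients. The protocol's only figure implies about 11–17%. A reader might also infer that returning patients alone know their diagnosis; same-day patients see the clinician first as well. Pooling patients treated or diagnosed before referral is a separate matter, whose analysis can be left to a SAP.

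**Conclusion.** The point holds as a limited design weakness that should be corrected. As written, the protocol lets the reference diagnosis alter some index features in late deciders, and lets it create a positive value for one critical feature.

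The expected effect on reversible features is slight: 0.80 to about 0.79 with 10% delayed, and to 0.76–0.77 with 30%. Steroid response is the more serious case, with a spurious odds ratio of about 1.1–1.3 and 1.2–2.1 respectively. These figures rest on an unstated delayed share, assumed response rates, treatment throughout the interval and no change in non-LS patients.

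That treatment starts within the window is an inference from Section 8 and the absence of any deferral; the protocol gives no start time. The documents do not support a stronger reading that the index test as a whole is compromised, or that the bias is known to be large.

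**What to change.** 1. In 3.3.1, define steroid response as response to treatment used before the specialist consultation.
2. In 6.1, record the interval between the two examinations and whether any treatment was started in it. Enforcing the two-week exclusion already requires both dates, so the added burden is small.
3. In 7.1, fit the primary model to pairs examined on the same day or before any treatment from that consultation was started. Add the remaining pairs in a sensitivity analysis, and report how many there are.

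Late deciders can still take part, and no change to clinical management is proposed. The cost is some pairs leaving the primary set: with 10% delayed, about 19 of 370 if only delayed LS patients were newly treated (0.10 × 185 = 18.5), and at most 37 if all delayed patients were (0.10 × 370). In the first case the LS share of the primary set moves from 50% to 166.5/351.5 = 47%, which is a further reason to report both sets.

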5.2 Eligibility Criteria

5.2.1 Inclusion criteria

- Female
- ≥18 years of age
- New presentation to a specialist clinic (secondary care or community hub) with a vulval skin complaint

5.2.2 Exclusion criteria

- Inability to provide informed consent
- Patients with surgical alteration of vulval skin as part of gender reaffirming surgery, or patients not born with a vulva
- More than 2 weeks since initial consultation from managing clinician

5.3 Expected duration of participant participation

Study participants participate in the study for approximately 30 minutes at a single study visit.

5.4 Participant withdrawal

Participants may be withdrawn from the study either at their own request or at the discretion of the Investigator. The participants will be made aware that this will not affect their future care. Participants will be made aware (via the PIS and consent form) that should they withdraw, the data collected to date cannot be erased and may still be used in the final analysis.

Participant data will be collected during the study visit when the diagnostic criteria assessment takes place. In the event that the participant withdraws from the study, all data collected by that point will be recorded in the CRF and where possible, the reason for withdrawal will be documented.

5.5 Informed consent

Informed consent will be obtained in accordance with the Research Ethics Committee guidance and Good Clinical Practice. Participant information will be developed involving patient representatives to ensure it is clear and easily understood. Potential participants will be allowed sufficient time to consider their participation. Same day research appointments will be available, but if patients request additional time to consider their involvement this will also be possible. The PIS will also cover what happens if a patient wishes to withdraw from the study.

All participants will provide written or digital informed consent. The Informed Consent Form will be signed and dated by the participant before entering the study. The Investigator or their nominee will explain the details of the trial and provide a PIS (either in advance of, or at the time of the outpatient clinic visit), ensuring that the participant has sufficient time to consider participating. The Investigator or their nominee will answer any questions that the participant has concerning study participation. As the study is low risk due to being non-interventional, we believe there will be sufficient time to consider participation for those who receive the PIS on the same day as their outpatient visit. This has the added benefit of being more convenient than coming back for another visit. However, potential participants will be given the opportunity to return on another occasion, within the next two weeks, if they wish (Figure 1).

If needed, hospital interpreter and translator services will be available to assist with the discussion of the study, the participant information sheets, and consent forms, but the consent forms and information sheets will not be available in other languages.

Clinical photographs will be taken as part of normal medical care. Participants will be asked specifically for consent to use the photographs for research purposes for development of a training manual which will be used at a later stage alongside the diagnostic tool to support its use.

Informed consent will be obtained from each participant before they undergo physical examination and have information collected for the study. Consent will primarily be completed online, but where a paper version is completed, this will be scanned and uploaded to REDCap. The participant will be provided a copy of this and it will be recorded in the medical record that consent for the study has been obtained.

Should there be any subsequent amendment to the final protocol which might affect a participant's participation in the trial, continuing consent will be obtained using an amended Consent Form which will be signed by the participant.

